6.7 Preparation and labeling of Investigational Medicinal Product

Preparation, labeling and dispensing of the CMV pp65-specific T cells will be performed at the IGFL as specified in SOPs according to GMP. Please refer to the IMPD.

6.8 Drug accountability

Procedures for shipment, receipt, disposition, return and destruction of the CMV pp65-specific T cells are specified in SOPs and will be performed by the IGFL according to GMP.

7. METHODS

7.1 Study endpoints

- The number of events of acute GvHD, death and all other adverse events.
- The number of CMV-specific T cells at different time points after infusion of CMV pp65-specific T cells.
- The number of complete responses or partial responses of CMV reactivation or CMV disease after infusion of CMV pp65-specific T cells.

7.2 Study procedures

7.2.1 Pretreatment investigations

- History, physical examination, WHO performance score (see Appendix A) and weight.
- CMV DNA load.
- Blood cell counts, differential, platelet count.
- Sodium, potassium, BUN, creatinine, liver enzymes, total bilirubin, albumin, LDH, glucose.
- Quantification of CMV-specific T cells by tetramer staining and functional assays (intracellular cytokine staining)
- Chest X-ray.
- Assessment of chimerism.

7.2.2 Investigations during treatment

Contraindications for administration of CMV pp65-specific T cells will be checked before the administration procedure of CMV pp65-specific T cells.

The product will be infused intravenously over 30 minutes via peripheral intravenous access, or, if already in place, an in-situ central venous access device. Actual doses of infused CMV pp65-specific cells will be documented.

Close monitoring of vital signs (temperature, pulse, respiratory rate, blood pressure, and oxygen saturation) will be measured and documented before CMV pp65-specific T cell infusion and every 15 minutes during a 1 hour period after infusion.

7.2.3 Investigation during follow-up in adults

- Interim history and physical examination including WHO performance score, weight, signs of toxicity, infection and GvHD daily during hospitalization or weekly for 8 weeks, followed by monthly for 4 more months.
- Blood cell counts, differential, platelet count, sodium, potassium, BUN, creatinine, liver enzymes, total bilirubin, albumin, LDH and glucose weekly for 8 weeks, followed by monthly for 4 more months.
- CMV DNA load at day 1 and 2, followed by weekly for 8 weeks and monthly for 4 more months.

- Quantification of CMV-specific T cells by tetramer staining and functional assays (intracellular cytokine staining) will be performed at the LUMC from blood samples from day 1 and thereafter weekly samples from week 1-8 and monthly samples from month 3-6.
- Assessment of chimerism at 6 weeks, 3 months and 6 months.

Weeks after infusion	0	1	2	3	4	5	6	7	8	12	16	20	24
Infusion of cells	x				(x)				(x)				
History and PE	x	x	x	x	x	x	x	x	x	x	x	x	x
Blood	x	x	x	x	x	x	x	x	x	x	x	x	x
CMV DNA	xxx	x	x	x	x	x	x	x	x	x	x	x	x
CMV tetramer	xx	x	x	x	x	x	x	x	x	x	x	x	x
Chimerism							x			x			x
xxx day 0, 1, 2													
xx day 0, 1													

The volume of blood for quantification of CMV-specific T cells by tetramer staining and functional assays (intracellular cytokine staining) is 50 ml.

The volume of bone marrow for chimerism analysis is 10ml.

7.2.4 Investigation during follow-up in children

- Interim history and physical examination including WHO performance score, weight, signs of toxicity, infection and GvHD daily during hospitalization or weekly for 8 weeks, followed by monthly for 4 more months.
- Sampling of blood will be according to study protocol “adoptive immunotherapy for adenovirus infections after allogeneic stem cell transplantation in children” as approved by the CCMO.

PBMC samples (20ml) will be taken and stored at 2 week intervals for the investigation of the presence and function of CMV-specific T cells until 3 months after last infusion. Blood sampling for this specific protocol will be combined with blood sampling for regular monitoring of the transplantation as much as possible.

7.3 Evaluation criteria

7.3.1 Safety evaluation after treatment

General non GvHD toxicity will be scored according to the NCI Common Terminology Criteria for Adverse Events (CTCAE) Version 4.0 (see appendix B) In case of grade 3 or 4 toxicity after infusion of CMV pp65-specific T cells, further administrations of CMV pp65-specific T cells will be cancelled in that patient.

Acute GvHD will be graded using the criteria outlined in appendix C. In case of grade 3 or 4 acute overall GvHD after infusion of CMV pp65-specific T cells, further administrations of CMV pp65-specific T cells will be cancelled in that patient.

7.3.2 Evaluation of clinical response

Complete response: Complete disappearance of CMV DNA load for at least 4 weeks.

Partial response: reduction of CMV DNA load of > 1 log but no complete disappearance of CMV DNA load for at least 2 weeks.

Stable disease: no significant change (<1 log) in viral DNA load and no complete disappearance of CMV DNA load for at least 4 weeks.

Progressive disease: persistent increase in CMV DNA load of > 1 log during 4 weeks or new CMV disease.

7.3.3 Evaluation of presence of CMV pp65-specific T cells

Quantification of CMV-specific T cells will be performed by tetramer staining and functional analysis of CMV-specific T cells by intracellular cytokine staining.

7.4 Withdrawal of individual subjects

Subjects can leave the study at any time for any reason if they wish to do so without any consequences. The treating clinician can decide to withdraw a subject from the study for urgent medical reasons.

7.5 Premature termination of the study

In case of increase of >1 point of overall grade acute GvHD in 2 out of the first 3 patients, or 3 out of the first 6 patients, or 4 out of the first 10 patients, the study will be closed temporarily for inclusions and the outcomes in all patients will be discussed in order to decide whether potential beneficial effects of the treatment could overcome non-beneficial effects of GvHD.

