In case of increase of >1 point of overall grade acute GvHD in 2 out of the first 3 patients, or 3 out of the first 6 patients, or 4 out of the first 10 patients, the study will be closed temporarily for inclusions and the outcomes in all patients will be discussed in order to decide whether potential beneficial effects of the treatment could overcome non-beneficial effects of GvHD.

End of study:

End of the study is defined as 6 months after the infusion of CMV pp65-specific T cells of patient number 15 or at time of subsequent DLI of patient number 15.

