5.2 Investigational treatment

CMV pp65-specific T cells are a cell therapy product that will be administered after alloSCT in case of CMV reactivation treatment failure or CMV disease. The CMV pp65-specific T cells will be generated from a CMV seropositive donor. The product will contain an aimed dose of $10\text{-}20 \times 10^6$ total T cells. This dose is based on the amount of cells we expect to isolate on the basis of the currently performed phase I/II clinical study (LUMC 2004-01) on the treatment of refractory CMV reactivation using CMV pp65-specific CD8+ T cells and preclinical data of the current strategy. All cells isolated will be infused if $\geq 20\%$ of the T cells are IFN γ and/or CD137 positive and the maximal amount of non-specific T cells in the product is $< 0.3 \times 10^6/\text{kg}$ body weight in patients transplanted with related donors and $< 0.15 \times 10^6/\text{kg}$ body weight in case of unrelated donors. If the number of non-specific T cells in the product exceeds these criteria, the infused dose will be adjusted accordingly. The cells will be administered intravenously at the department of Hematology of the LUMC. In case of ongoing CMV reactivation or CMV disease and no severe toxicity, the procedure may be repeated 2 times with at least 4 weeks interval.

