5.4 Contraindications for administration of CMV pp65-specific T cells

- Life expectation < 6 weeks.
- End stage irreversible multi-system organ failure.
- Acute GvHD overall grade \geq III.
- Treatment with corticosteroids in an equivalent dose of >0.5 mg/kg prednisone.
- No CMV reactivation or CMV disease.

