8. SAFETY REPORTING

8.1 Section 10 WMO event

In accordance to section 10, subsection 1, of the WMO, the investigator will inform the subjects and the CCMO if anything occurs, on the basis of which it appears that the disadvantages of participation may be significantly greater than was foreseen in the research proposal. The study will be suspended pending further review by the CCMO, except insofar as suspension would jeopardize the subjects' health. The investigation will take care that all subjects are kept informed.

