9.5 Interim analysis

After the first 3, 6 and 10 patients an interim analysis will be performed by the principal investigator.

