APPENDIX C

Grading of GvHD

Acute GvHD

Staging of acute GvHD

	Skin	Liver	Gastrointestinal
0	No rash	Bilirubin < 2 mg / dl (< 34 umol/L)	Diarrhea < 500 ml/day
1	Maculopapular rash on < 25% of body surface	Bilirubin 2-3 mg/dl (34-50 umol/L)	Diarrhea 500-1000 ml/day
2	Maculopapular rash on 25-50% of body surface	Bilirubin 3-6 mg/dl (51-102 umol/L)	Diarrhea 1000-1500 ml/day
3	Generalized erythroderma	Bilirubin 6-15 mg/dl (103-225 umol/L)	Diarrhea > 1500 ml/day
4	Generalized erythro- derma with formation of bullae and desquamation	Bilirubin > 15 mg/dl (> 225 umol/L)	Severe abdominal pain with or without ileus

Grading of acute GvHD

Overall grade	Stage		
	Skin	Liver	Gut
I (mild)	1 or 2	0	0
II (moderate)	1-3	1	1
III (severe)	2 or 3	2 or 3	2 or 3
IV (life-threatening)	2-4	2-4	2-4

Chronic GvHD

Limited Localized skin involvement and/or liver function abnormalities

Extensive Generalized skin involvement or localized skin involvement and/or liver function abnormalities + other organ involvements

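### The acute GvHD pause rule in 7.5 does not count a worsening from grade II to grade III, although 5.4 allows infusion at grade II

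*Protocol*

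**What the plan says.** Section 7.5 of the protocol, repeated in the summary, sets the study-level rule for acute GvHD: "In case of increase of >1 point of overall grade acute GvHD in 2 out of the first 3 patients", or in 3 of the first 6, or in 4 of the first 10. The consequence is that "the study will be closed temporarily for inclusions and the outcomes in all patients will be discussed". It is a pause followed by a discussion, not a termination.

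Who may be infused is fixed in 5.4. The GvHD contraindication there is overall grade III or higher. A further item is "Treatment with corticosteroids in an equivalent dose of >0.5 mg/kg prednisone". The exclusion criteria in 4.3 contain no GvHD item. Section 5.2 adds that "the procedure may be repeated 2 times with at least 4 weeks interval", so a patient may have up to three infusions.

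Elsewhere the protocol uses grade III as its line for serious GvHD. Section 7.3.1 cancels further infusions in the patient: "In case of grade 3 or 4 acute overall GvHD after infusion of CMV pp65-specific T cells". Section 9.4 tabulates acute GvHD of grade III or more as treatment toxicity. Appendix C labels grade II moderate and grade III severe.

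**The concern.** The pause rule measures change only, and its step is two grades. For a patient infused without GvHD or with grade I, any move to grade III or IV is at least two grades and is counted. For a patient infused at grade II, a move to grade III is one grade and is not counted. The study-level rule therefore gives weight to a new moderate case and none to a new severe case in a patient who already had GvHD at infusion.

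Acute GvHD is the risk named in 10.3, and 7.5 is the only numerical study-level boundary in the protocol. With thresholds of 2 of 3, 3 of 6 and 4 of 10, one uncounted patient can decide whether inclusion pauses.

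A smaller point lies in the same sentence: 7.5 does not name the grade from which the increase is measured, although a patient may be infused three times.

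**Working it through.** The protocol states no operating characteristics for this rule, so there is no figure of its own to reproduce.

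**Step 1: which changes count.** Inputs: baseline grades allowed at infusion are 0, I and II (5.4); the scale is whole grades up to IV (Appendix C); an event is a rise of more than one grade (7.5).

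| Grade before infusion | Grade after | Rise | Counted in 7.5 | Ends in III or IV |
|---|---|---|---|---|
| 0 | I | 1 | no | no |
| 0 | II | 2 | yes | no |
| 0 | III | 3 | yes | yes |
| 0 | IV | 4 | yes | yes |
| I | II | 1 | no | no |
| I | III | 2 | yes | yes |
| I | IV | 3 | yes | yes |
| II | III | 1 | **no** | **yes** |
| II | IV | 2 | yes | yes |

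Six changes end in grade III or IV. The rule counts five and misses one, II to III. It counts 0 to II, which ends in moderate GvHD.

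**Step 2: the reference grade.** Take a patient who goes from 0 to I after the first infusion and from I to II after the second. From the grade before the first infusion the rise is 2 and counts. From the grade before the latest infusion it is 1 and does not.

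**Step 3: effect on the chance of a pause.** Let q be the probability that a patient is a counted event, with patients independent. A pause occurs if there are at least 2 events in 3 patients, 3 in 6 or 4 in 10. The exact calculation at an assumed q = 0.20:

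- At 3 patients: 3 × 0.2² × 0.8 + 0.2³ = 0.104. Still open: 0.512 with no event, 0.384 with one.
- At 6 patients: 0.512 × 0.008 + 0.384 × 0.104 = 0.044. Still open: 0.2621, 0.3932 and 0.1966 with 0, 1 and 2 events.
- At 10 patients: 0.2621 × 0.0016 + 0.3932 × 0.0272 + 0.1966 × 0.1808 = 0.0467.
- Total: 0.104 + 0.044 + 0.0467 = 0.1947.

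If II to III were counted, the added rate would be the share of patients infused at grade II times the share of those who worsen to III. The protocol gives neither share. Assume 20% worsen and 5%, 10%, 20% or 30% are infused at grade II; the added rate is then 1%, 2%, 4% or 6% of all patients.

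| Added rate | Pause by patient 10, counted rate 10% | Pause by patient 10, counted rate 20% |
|---|---|---|
| 0 (rule as written) | 4.1% | 19.5% |
| 1% | 5.1% | 21.6% |
| 2% | 6.2% | 23.8% |
| 4% | 8.8% | 28.5% |
| 6% | 11.9% | 33.5% |

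For added rates of 2%, 4% and 6% the increase is 2.1, 4.7 and 7.8 percentage points at a counted rate of 10%, and 4.4, 9.1 and 14.0 points at 20% (differences taken before rounding).

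**The case against.** **Oversight does not depend on the count.** Section 9.5 says "After the first 3, 6 and 10 patients an interim analysis will be performed by the principal investigator", which are the same looks as in 7.5 and take place whatever the count. Section 9.4 would tabulate the grade III event, 8.2 would report it if it met a seriousness criterion, and 7.3.1 would stop further infusions in that patient. If harm exceeded expectation, 8.1 applies: "The study will be suspended pending further review by the CCMO". This stands as far as detection goes. A reader might infer that the trial would overlook severe GvHD in patients infused at grade II, and the protocol does not support that. But 9.5 states no GvHD criterion, 8.1 rests on judgement, and none of these sections adds the event to the count in 7.5.

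**It may be a deliberate choice.** A change criterion limits the counting of fluctuation in GvHD that was present before infusion, and it treats all one-grade steps alike. That is a fair reason to ignore 0 to I and I to II. It is a weaker reason to ignore a step that crosses the severity line used in 5.4, 7.3.1 and 9.4.

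**The reference grade is fairly clear.** The rule counts patients and not infusions, so change from before treatment is the natural reading, and 7.2.2 has contraindications, which include the GvHD grade, checked before administration. This largely stands; the point is a minor clarification.

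**Appendix C.** A reader might go further and say that the grading table makes the event undecidable, or that the fix would remove grading ambiguity. Neither should be claimed. The table was read from PDF and connecting words may be lost. If the organ columns are read as alternatives, the rows for II and III overlap too, so a trigger at grade III would still depend on how grades are assigned.

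**Conclusion.** The gap is real and follows from the text of 5.4, 7.5 and Appendix C without any assumption: of the six worsenings to grade III or IV that are possible from an allowed baseline, the pause rule leaves out II to III. What is lost is an automatic contribution to a temporary pause, not detection of the event.

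The practical size is unknown. It depends on how many patients are infused at grade II and how many of them worsen, and the protocol gives neither. Over the assumed ranges above, the chance of a pause by patient 10 differs by about 1 to 14 percentage points. A reader might picture the extreme in which all of the first 10 patients go from II to III and the count stays at 0. That is a logical limit of the rule; nothing in the protocol suggests it is likely.

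This is a cheap improvement to a safety rule. It does not show that the trial is unsafe as planned.

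**What to change.** In 7.5 and in the matching paragraph of the summary, define the event as either (a) an increase of more than one point over the overall acute GvHD grade recorded before the first infusion, or (b) any new overall grade III-IV acute GvHD after infusion. Measured against the grade before the first infusion, part (b) adds only the change from II to III, because every other move to III or IV from an allowed baseline already counts. Part (a) settles the reference grade in the same sentence. The thresholds of 2 of 3, 3 of 6 and 4 of 10 can stay, as can 5.4, 7.3.1 and 9.4.

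The cost is a wording change in two places and somewhat more frequent temporary pauses. On the assumed rates, an added 2% to 6% of patients means 2.1 to 7.8 percentage points more at a counted rate of 10%, and 4.4 to 14.0 points more at 20%. Each pause leads to a discussion of benefit against GvHD, not to closure of the trial.

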4. STUDY POPULATION

4.1 Population

- Recipients of alloSCT (age 0-75 years) with CMV reactivation who fail antiviral therapy (defined as **CMV reactivation treatment failure**: persistent CMV DNA load of more than 1000 cp/ml or CMV disease after 2 weeks of adequate treatment with antiviral therapy or relapse of CMV DNA load of more than 1000 cp/ml within 4 weeks after adequate treatment with antiviral therapy or contraindication for treatment with antiviral therapy at the discretion of the physician) **or**
- Patients who develop **CMV disease** (organ dysfunction (pneumonitis, enteritis, retinitis, encephalitis, hepatitis, and bone marrow suppression) due to CMV infection).
- Number of patients to be treated with CMV pp 65 specific T cells will be 15.

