9.2 Planned sample size

We aim to include 15 patients. On the basis of the currently performed phase I/II clinical study (LUMC 2004-01) on the treatment of refractory CMV reactivation we expect to include 5-7 patients per year for a period of 3 years.

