9.3 Power calculation

We consider the infusion of CMV pp65-specific T cells a success when the response rate is at least 66 % (p_1 ; 2/3 of patients). Based on our historical experience, we estimate the rate of responses with pharmacotherapy alone but without immune intervention to be 30% ($=p_0$) for the targeted patient population. Given the high laboratory effort and associated costs of treatment with CMV pp65-specific T cells, the trial should have a power of 90% (beta-error 0.1). With the usual alfa-error of 0.05, the sample size as calculated according to the standard Fleming design is 15 treated patients under these assumptions. We expect no excess in number of events of acute GvHD, death and all other adverse events.

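### The numeric acute GvHD pause rule and its scheduled looks end at patient 10 of 15; carrying the rule on is a minor, cheap improvement

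*Protocol*

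**What the plan says.** Section 7.5 of the protocol sets the only numeric study-level rule for acute GvHD. It begins "In case of increase of >1 point of overall grade acute GvHD in 2 out of the first 3 patients" and continues with "3 out of the first 6 patients, or 4 out of the first 10 patients, the study will be closed temporarily for inclusions". Outcomes in all patients are then discussed to weigh benefit against GvHD. The summary repeats the same three counts ("in 2 out of the first 3 patients, or 3 out of the first 6 patients, or 4 out of the first 10 patients").

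Section 9.5 sets the timing: "After the first 3, 6 and 10 patients an interim analysis will be performed by the principal investigator". No later look is planned. The trial goes on to 15: "Number of patients to be treated with CMV pp 65 specific T cells will be 15" (4.1).

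No GvHD rate is given. Section 9.3 says only "We expect no excess in number of events of acute GvHD, death and all other adverse events".

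Three other safety provisions matter here:
- Section 7.3.1 cancels further infusions in the individual patient who develops severe toxicity or GvHD.
- Section 8.1 suspends the study if the disadvantages prove significantly greater than foreseen.
- Sections 8.2 and 8.2.2 require SAE reports and an annual safety analysis.

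**The concern.** The inputs to the rule are the outcomes of patients 1-3, 1-6 and 1-10. Once the first ten have been counted with three events or fewer, nothing that happens in patients 11-15 can meet it. The sponsor wanted a fixed count for the first ten patients and gives no reason for having none for the last five.

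This produces an uneven result. Four events in ten patients (40%) close inclusion. Three in the first ten followed by events in patients 11, 12 and 13 make 6/13 (46%), and patients 14 and 15 can still be included without a numeric prompt. Acute GvHD is the one risk named in 10.3 and comes first in the safety endpoint (7.1), so the gap deserves a check.

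**Working it through.** **Inputs.** Boundaries are 2/3, 3/6 and 4/10 (7.5), looks come after 3, 6 and 10 patients (9.5), and 15 patients are treated (4.1). I read each boundary as at least that many. The documents give no event rate, so I assume true rates p of 10% to 60%, with independent patients and q = 1 - p.

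**The plan's own figure.** The rule has no stated operating characteristics to reproduce. The sample size does reproduce. With p0 = 0.30, p1 = 0.66, one-sided alpha 0.05 and power 0.90 (9.3), n = ((1.645×√0.21 + 1.282×√0.2244)/0.36)² = 14.29, rounded up to 15. So patients 11-15 are 5/15 = 33% of the trial.

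**Largest unpaused count.** At most 3 events in the first 10, plus 5 more, gives 8/15 = 53%.

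**Chance of no pause.** I counted the sequences of ten outcomes that avoid all three boundaries:
- 0 events: 1 sequence.
- 1 event: 10.
- 2 events: 45 - 3 = 42 (removing both events in the first three).
- 3 events: 120 - 22 - 10 = 88 (removing two or more in the first three, then the remaining cases with all three in the first six).

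P(no pause) = q¹⁰ + 10pq⁹ + 42p²q⁸ + 88p³q⁷. At p = 0.4 this is 0.0060 + 0.0403 + 0.1129 + 0.1577 = 0.317.

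**Unpaused with a high final count, p = 0.4.** Among five further patients, P(at least 3) = 0.3174, P(at least 4) = 0.0870 and P(5) = 0.0102.
- At least 6/15: 0.1577×0.3174 + 0.1129×0.0870 + 0.0403×0.0102 = 0.060. Given no pause: 0.060/0.317 = 19%.
- At least 7/15: 0.1577×0.0870 + 0.1129×0.0102 = 0.015.

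**Carrying 4 in 10 forward.** In whole patients, 40% means 5 of 11, 5 of 12, 6 of 13 and 6 of 14. A trial that passes patient 10 has at most 3 events, so at most 4 at patient 11, and 5/11 is unreachable. A trial that passes 5/12 has at most 4, so at most 5 at patient 13, and 6/13 is unreachable. Only 5/12 and 6/14 can fire. At p = 0.4:
- At patient 12: 0.1577×0.16 = 0.0252.
- At patient 14: (0.1577×2×0.4×0.6 + 0.1129×0.16)×0.16 = 0.0150.
- Total 0.0402, so the chance of a pause goes from 0.683 to 0.723. Of the trials that were unpaused, 0.0402/0.317 = 13% are now paused.
- Mean inclusions held back: 0.0252×3 + 0.0150×1 = 0.09 patients.

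The same steps at each rate give:

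| True rate | Pause, current rule | Unpaused and ≥6/15 | Unpaused and ≥7/15 | ≥6/15 given unpaused | Pause with 5/12 and 6/14 added |
|---|---|---|---|---|---|
| 10% | 4.10% | 0.04% | <0.01% | 0.05% | 4.15% |
| 20% | 19.5% | 1.1% | 0.1% | 1.3% | 20.3% |
| 30% | 43.7% | 3.9% | 0.7% | 6.9% | 46.4% |
| 40% | 68.3% | 6.0% | 1.5% | 19% | 72.3% |
| 50% | 86.2% | 5.1% | 1.7% | 37% | 89.7% |
| 60% | 95.7% | 2.5% | 1.1% | 58% | 97.5% |

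**Time to act.** Section 9.2 says "we expect to include 5-7 patients per year for a period of 3 years". Five patients at 7 per year take 5/7×12 = 8.6 months, and at 5 per year 12 months.

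**The case against.** The strongest reply is that the gap seldom matters. When the true rate is high, the first ten patients usually trigger the rule, so an unpaused trial that ends above 40% (at least 7/15) has probability under 2% at every rate tried. The added boundaries hold back less than a tenth of an inclusion on average, even if GvHD is known at once, and a pause at patient 14 protects one person. This stands, and it limits the point to a minor one.

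It is also fair that the rule's power is settled mainly by its first-ten boundaries. At a true rate of 40% the chance of never pausing falls only from 31.7% to 27.7% with the extension.

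A reader might infer that patients 11-15 have no study-level protection. The documents do not support that. Section 8.1 can suspend the study at any time, SAEs are reported within 15 days (7 if fatal or life-threatening), and a full safety analysis is due each year. In addition, 7.5 does not restrict the count to events seen by the interim date, so a late event in patients 1-10 could still meet the rule while later patients are being included. What these provisions lack is a GvHD threshold or a scheduled count that includes patients 11-15.

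A reader might also take 40% as the protocol's maximum tolerable rate. The protocol states counts, whose proportions fall from 67% to 50% to 40%, and names no such maximum. Carrying 4 in 10 forward is a reading of the last count.

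**Conclusion.** The point holds as a minor one. Sections 7.5 and 9.5 and the summary agree with one another, and all end the numeric GvHD rule at patient 10, leaving one third of the trial outside it. Overall the consequence is small: about 1-6% for an unpaused trial at 6/15 or more, over assumed true rates of 20-60%. It is larger among trials that pass patient 10 unpaused, where 6/15 or more follows with probability 7%, 19% and 37% at true rates of 30%, 40% and 50%. All these figures rest on assumed rates and independent patients.

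It would go too far to say that an uncrossed rule will be presented as proof of no excess GvHD. The statement in 9.3 is an expectation, and nothing in the protocol treats not crossing the rule as evidence of safety. Nor is the lack of an upper confidence bound in 9.4 a fault, since that is commonly left to the statistical analysis plan.

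**What to change.** In 7.5, 9.5 and the summary, add two counts to the existing rule: 5 of the first 12 and 6 of the first 14. Keep the same event and the same consequence, temporary closure to inclusion and discussion. Leave out 5 of 11 and 6 of 13, which cannot occur once the other boundaries have been passed. In the example above, the pause would come at patient 12 (5/12), before patient 13 is included, provided the event is known by then.

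The cost is a short wording amendment and two further counts of data already collected, with no extra patients or procedures. Additional pauses at low rates are few: 0.05 percentage points at a true rate of 10% (4.10% to 4.15%) and 0.8 points at 20% (19.5% to 20.3%). The gain is limited too, since a pause this late protects only the patients not yet included: three at most after patient 12 and one after patient 14.
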